## 1.0 Background

[figure not shown]
**A. Definition of DIH.** Various definitions have been used for intradialytic hypotension. The National Kidney Foundation Kidney Disease Outcome Quality Initiative (K/DOQI) has defined DIH as a reduction in systolic blood pressure or mean arterial pressure during hemodialysis, which it is associated with symptoms such as muscle cramps, anxiety, yawning, dizziness, fainting, or abdominal discomfort. The reduction in blood pressure should be equal to or greater than 20 mmHg for systolic blood pressure and equal to or greater than 10 mmHg for mean arterial blood pressure. Most of the reduction of blood pressure during hemodialysis occurs during the first quarter of treatment with a gradual decrease during the remaining treatment time (**Figure 1**). Some investigators use a nadir-based DIH definition—when the systolic blood pressure

falls below 90 or 100 mmHg., or the need for nursing intervention in addition to experiencing a fall in blood pressure and clinical symptoms. The reduction in blood pressure can also be asymptomatic. Thus, it is important to recognize the occurrence of repeated episodes of hypotension that will damage organs including the brain, heart, gut, and liver as well as skeletal muscle. Furthermore, it is important to identify patients who are susceptible to intradialytic hypotension to prevent the undesirable consequences of DIH.

**B. Morbidity and mortality of DIH.** Approximately 75% of patients suffer at least one episode of hypotension during hemodialysis, and DIH occurs in approximately 20 to 30% of all regular hemodialysis treatments. DIH is a common clinical complication of hemodialysis, and it is associated with increased morbidity and mortality. It has been shown that DIH may induce myocardial dysfunction due to reduced myocardial blood flow. Recurrent episodes of hypotension are also associated with frontal lobe atrophy in the brain, and with mesenteric ischemia. Previous studies have identified an association between DIH and cardiovascular morbidity-mortality, and all-cause mortality. Two more recent studies, using large databases, also showed the association between DIH and mortality.

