## **5.0 Enrollment/Randomization**

This is a parallel study where participants will be assigned to either taking the study drug (lanadelumab) or taking the placebo (saline pre-filled syringes.) Patients will be randomly assigned to the treatment order using a permuted-block randomization algorithm. The study drug, lanadelumab, will be shipped from Takeda as pre-filled syringes along with matching placebo, also in prefilled syringes. The Vanderbilt Investigational Drug Services (IDS) will be responsible for the storage, preparation, dispensing, and labeling of the investigational agents. The Vanderbilt IDS will also maintain accurate drug storage and dispensing logs. Subjects will be randomized to receive a placebo or 300 mg of lanadelumab (Takeda Pharmaceutical, Cambridge, MA). Subjects randomized who do

not complete the whole protocol for any reason will be replaced, and their data will be analyzed separately. The half-life of lanadelumab is 14 days, and the time to reach maximum concentration is five days. For this reason, we will monitor blood pressure and the occurrence of DIH for three weeks after the administration of the second dose of the study drug.

[figure not shown]

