### **Hemodialysis**

All subjects will be dialyzed with their usual prescription. The duration of the dialysis treatment will vary between subjects, but it will be the same as the usual standard of care. Dialysis will be performed with biocompatible polysulfone membranes (Fresenius F80-A, Walnut Creek, CA). We will use new dialyzers on each study day. Dialyzers will be stored for further analysis of the proteins adsorbed to the membrane.

Crit-Lines®, which monitors hematocrit, percent change in blood volume, and oxygen saturation during hemodialysis, will be applied every hemodialysis session during the study if the device is available and the nursing staff is trained appropriately.

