### **Hemodynamic measurements**

During the baseline visit, we will obtain three supine blood pressure measurements. During hemodialysis study days, blood pressure will be taken in the arm contralateral to the access for dialysis using an automated oscillometric recording device. We will obtain three measurements during a period of 15 minutes before starting dialysis. The average of these measurements will be considered the baseline blood pressure. During hemodialysis, we will obtain blood pressure every 15 minutes. At the end of hemodialysis, we will obtain two more blood pressure measurements that will be averaged to obtain the post-dialysis blood pressure

Table2. CRC study visit

• Physical exam and history

• Body composition - physical performance tests

• QOL questionnaire/recovery time

• Study drug administration

-------------------------------------------------------------------------------------------------------------------------------------------------------------------------------------------------------------------

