## **10.0 Statistical Considerations**

### ***a. Sample size***

The primary outcome will be the change in blood pressure during hemodialysis. For this, we will average blood pressure during hemodialysis of three hemodialysis sessions within the second week of treatment. Secondary endpoints will also be recorded during the second week of treatment and will include the number of hypotensive events, frequency of nursing interventions, average of dialysis recovery times, and average symptoms severity score. Based on our preliminary studies with icatibant and assuming a standard deviation of differences of 13.6 mmHg (pooled SD of the delta), a sample size of 16 in each arm will have 80% power to detect a difference in means of -13.7 mmHg, using a paired t-test with a 0.05 two-sided significance level.

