### ***b. Data analysis plan***

Standard graphing and screening techniques will be used to detect outliers and to ensure data accuracy. Distributions of the continuous outcomes will be assessed for normality. If normality is violated, proper data transformation will be applied, or non-parametric analysis methods will be considered. The primary endpoints are SBP and DBP. The secondary endpoints include heart rate, and the R-R interval (autonomic function), the time to recover after HD, symptoms associated with DIH, and the distance walked during the six-minute walk test.

Mixed effect models will be used to analyze the primary endpoint (blood pressure) with a random subject effect and with the treatment (lanadelumab vs placebo) and the time trend (measurements every 15 minutes) as fixed effects. The focus of this study will be the treatment effect and the time trend of the endpoints; however, mixed effect models also provide the flexibility of controlling for and evaluating covariates. However, we will be careful not to over-fitting the model due to the limited sample size.

Besides the above evaluation of the treatment effect and the time trend through the regression models, the direct treatment effect will also be estimated as within-subject mean difference along with their 95% confidence intervals. For the secondary endpoints, a paired t-test will be performed (lanadelumab vs placebo). If the normality of the data is violated, we will use non-parametric tests.

For binary endpoints (e.g., occurrence of hypotensive events), we will use the McNemar test to compare lanadelumab and placebo.

**Missing Data.** Based on our previous studies, we anticipate a drop-out rate of 10% or less. Subjects who drop out will be replaced. Specific inferences on effects of interest will be made by reporting a point estimate along with a 95% confidence interval and the p-value. Hypotheses will be tested at the level of  $\alpha=0.05$ . We will use SPSS (version 25.0, SPSS, Chicago, IL) and the open-source statistical package R (R Core Team, 2017) for analyses.

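### The primary mixed model names only a random subject effect for readings taken every 15 minutes, so the standard error of the time trend, one of its two stated targets, is likely to be understated.

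*Combined protocol and SAP*

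**What the plan says.** Section 10.0, Data analysis plan, gives the primary model "with a random subject effect and with the treatment (lanadelumab vs placebo) and the time trend (measurements every 15 minutes) as fixed effects". It then sets the targets: "The focus of this study will be the treatment effect and the time trend of the endpoints". The Missing Data paragraph of the same section promises an estimate, a 95% confidence interval and a p-value for each effect of interest.

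On the data that feed the model, Hemodynamic measurements says "During hemodialysis, we will obtain blood pressure every 15 minutes". The Sample size paragraph says "we will average blood pressure during hemodialysis of three hemodialysis sessions within the second week of treatment". The Hemodialysis section says "The duration of the dialysis treatment will vary between subjects" and gives no length in hours. Section 1.0 says of the shape of the curve: "Most of the reduction of blood pressure during hemodialysis occurs during the first quarter of treatment".

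The only limit placed on the model is a general caution about over-fitting. The form of time (line or factor), the covariance structure and the unit of data (raw sessions or an averaged profile) are not stated.

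**The concern.** A model with one random intercept per patient treats all of a patient's readings as equally correlated, whatever their spacing or session. Intradialytic pressure is unlikely to behave that way. Patients differ in how fast pressure falls, and readings 15 minutes apart tend to resemble each other. Either feature makes the estimated time trend more variable than the model reports, because the model counts many within-patient readings as nearly independent evidence about a slope that really varies between only 32 patients.

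The trend is not a nuisance term here, since the plan names it as a target and promises an interval and a p-value for it. If the model is fitted as written, that interval would claim more precision than the trial has.

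**Working it through.** **Inputs from the protocol.** 32 patients (16 per arm), readings every 15 minutes, three sessions, and an SD described as "assuming a standard deviation of differences of 13.6 mmHg (pooled SD of the delta").

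**Assumptions.** A 4-hour session (16 readings, at 0.25 to 4 h), a linear trend, session-level SD 6 mmHg when raw sessions are used, AR(1) residuals with lag-1 correlation ρ, balanced data and no dropout. f is the share of the variance of the end-minus-start change that comes from patients' slopes differing. The documents give neither f nor ρ.

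**Step 1: the plan's own figure.** n per arm = 2 × (1.96 + 0.8416)² × 13.6² / 13.7² = 2 × 7.849 × 184.96 / 187.69 = 15.5, rounded up to 16. So 16 per arm reproduces with a two-sample formula (exact t-test power 78.7%). The paired test that the text names would have 96.4% power with 16 pairs; that is a separate matter. The plan gives no precision figure for the time trend.

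**Step 2: scale to 13.6 mmHg.** Set 13.6² = (4·s_b)² + 2·s_e², where s_b is the SD of patient slopes and s_e the SD of a reading. Then s_b = √f × 13.6/4 and s_e² = (1 − f) × 13.6²/2. For f = 0.25, s_b = 1.70 mmHg/h and s_e² = 69.36 (s_e = 8.33).

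**Step 3: true standard error.** The spread of the reading times is Sxx = 0.25² × 16 × (16² − 1)/12 = 21.25. The variance of the mean slope is (s_b² + v/3)/32, where v is the slope variance from one session (s_e²/Sxx when ρ = 0, larger when ρ > 0). For f = 0.25 and ρ = 0, v = 69.36/21.25 = 3.264. The variance is (2.89 + 1.088)/32 = 0.1243, so the SE is 0.353 mmHg/h.

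**Step 4: SE reported by the random-intercept model.** Sum of squares per patient around the patient mean:
- readings: 69.36 × 47 = 3259.9
- session levels: 36 × 32 = 1152
- slopes: 2.89 × 63.75 = 184.2

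The total is 4596. The residual variance is (32 × 4596.2 − 0.1243 × 2040)/1503 = 97.7, where 2040 = 32 × 3 × 21.25 and 1503 = 32 × 47 − 1. The reported SE is √(97.7/2040) = 0.219. The ratio is 0.353/0.219 = 1.61, and coverage is 2Φ(1.96/1.61) − 1 = 78%.

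**Step 5: range of assumptions.** True SE divided by reported SE, with coverage of a nominal 95% interval:

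| f | ρ | Three raw sessions | One averaged profile |
|---|---|---|---|
| 0 | 0 | 0.89 (97%) | 1.00 (95%) |
| 0 | 0.5 | 1.36 (85%) | 1.61 (78%) |
| 0.10 | 0.3 | 1.39 (84%) | 1.41 (83%) |
| 0.25 | 0.3 | 1.76 (74%) | 1.58 (78%) |
| 0.50 | 0.3 | 2.39 (59%) | 1.96 (68%) |
| 0.75 | 0.5 | 3.23 (46%) | 2.71 (53%) |

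The right-hand column puts the 13.6 mmHg on the averaged profile. If 13.6 belongs to a single session, averaging cuts the reading variance to a third and leaves the slope differences untouched. For f = 0.25 and ρ = 0 the true SE stays at 0.353. The residual variance becomes [32 × (23.12 × 15 + 2.89 × 21.25) − 0.1243 × 680]/479 = 27.1, so the reported SE is √(27.1/680) = 0.200 and the ratio is 1.77, against 1.61 with raw sessions.

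**Step 6: simulation.** Assumed patient SD 12, session SD 8, residual SD 9, ρ = 0.4, and slope SDs of 1, 2 and 3 mmHg/h for patient and for session. Trend coverage was 83%, 69% and 56% with raw sessions, and 75%, 61% and 53% with one averaged profile. Inference from patient-level slopes restored about 95%. In separate mixed-model fits (300 runs per scenario), coverage for the treatment main effect was 93–95%.

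**Step 7: shape of the trend.** Suppose, as an illustration, that 18 of a 30 mmHg fall over 4 h comes in the first hour. The slope is then 18 mmHg/h, followed by (30 − 18)/3 = 4 mmHg/h. One least-squares line through readings every 15 minutes from 0 to 4 h has a slope of 6.4 mmHg/h, which describes neither part.

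**The case against.** The case against has five parts.

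- **The text does not say intercept only.** That is right: an intercept is the natural reading, but an inference. If something richer is meant, the plan must say so, and the same edit settles it.
- **Three sessions of 16 readings is not established.** This stands. The Sample size paragraph speaks of averaging. The 15-minute readings are promised for study days, and Appendix A lists one dialysis visit in the week before the second dose (Day 13) and two shortly after it (Days 15 and 17). Other sessions rely on clinic logs with no stated interval. But the problem remains with one averaged profile. Only collapsing to a single mean per patient would remove it, and that leaves no 15-minute trend to fit.
- **The size is assumed.** This stands. A reader might infer that the intervals are bound to be far too narrow. The documents do not support that, because they give neither slope variance nor autocorrelation. In the widest simulated setting, slopes alone imply a change SD of 3 × √2 × 4 = 17 mmHg, above 13.6 if that figure is for a single session.
- **The trend would be significant anyway.** Probably so: 6.4 mmHg/h against the largest simulated true SE of 0.67 is 9.6 standard errors from zero. The damage is to the interval, which the plan promises to report.
- **Over-fitting.** The caution follows a remark on covariates. One random slope for 32 patients is modest. AR(1) residuals or Kenward-Roger corrections are not needed to restore coverage in the cases examined.

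**Conclusion.** The concern holds in limited form. Fitted as written, the model understates the standard error of the time trend unless all patients share one slope and successive readings are uncorrelated. Under moderate assumptions (f 0.10 to 0.50, ρ 0.3, raw sessions) the factor is about 1.4 to 2.4, with coverage of 84% to 59%. With 13.6 mmHg placed on an averaged profile, the same assumptions give 1.4 to 2.0. The full range examined is 0.9 to 3.2.

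Three stronger conclusions are tempting but not supported:

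- **The lanadelumab-versus-placebo test is invalid.** In a parallel design ("This is a parallel study where participants will be assigned to either taking the study drug (lanadelumab) or taking the placebo") with balanced data, the treatment main effect keeps about its nominal coverage. Unequal session lengths were not simulated.
- **The trial will find false differences in trajectory.** In one set of assumed simulations, a treatment-by-time test rejected 15% to 39% of the time under no effect. The plan writes no such term. It would share the problem if it were added.
- **The plan fits a straight line.** It does not say so. Naming 15-minute measurements is equally consistent with a factor, so Step 7 is a warning about an unstated choice.

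This should be corrected before the analysis, but it does not undermine the treatment comparison.

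**What to change.** In the Data analysis plan:

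1. State what enters the model: raw 15-minute readings from each session, or one averaged 15-minute profile per patient.
2. Add a patient-level random slope for time to the random intercept, or use patient-clustered small-sample standard errors. Name the clustered errors as the fallback if the model does not converge.
3. If raw sessions enter, add a random effect for session within patient.
4. Enter time as the 15-minute factor, or as piecewise-linear with a knot at one quarter of the session, to match the early fall described in section 1.0. With the factor as the fixed effect, keep the random slope on continuous time.
5. If a comparison of trajectories between arms is wanted, write the treatment-by-time term down and use the same random structure.

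The cost is a sentence or two of text and a few lines of code, with no new data. The model becomes slightly more complex for 32 patients. Trend intervals widen to their proper width: for f = 0.25 and ρ = 0.3 with raw sessions, the half-width goes from 1.96 × 0.22 = 0.43 to 1.96 × 0.38 = 0.74 mmHg/h.

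### Secondary, binary and supplementary treatment comparisons are specified as paired analyses in a parallel-group trial that has no pairs, and the power sentence names a paired t-test although its figures are two-sample

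*Combined protocol and SAP*

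**What the plan says.** **Design.** Section 5.0 says: "This is a parallel study where participants will be assigned to either taking the study drug (lanadelumab) or taking the placebo". Section 6.0 likewise describes a parallel-group trial with two doses of one or the other product. Appendix A shows one course, dosed on Days 0 and 14, with no second treatment period. Allocation is by permuted blocks, and no matching of patients is described anywhere. One phrase in Section 5.0 does not fit this design: "Patients will be randomly assigned to the treatment order".

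**Analysis.** Section 10.0 b names three paired methods for comparing the treatments:
- Secondary endpoints: "For the secondary endpoints, a paired t-test will be performed (lanadelumab vs placebo".
- Binary endpoints such as the occurrence of hypotensive events: "we will use the McNemar test to compare lanadelumab and placebo".
- Supplementary estimate: "the direct treatment effect will also be estimated as within-subject mean difference along with their 95% confidence intervals".

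The primary blood-pressure analysis is a mixed model "with a random subject effect and with the treatment (lanadelumab vs placebo) and the time trend (measurements every 15 minutes) as fixed effects".

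**Sample size.** Section 10.0 a proceeds by "assuming a standard deviation of differences of 13.6 mmHg (pooled SD of the delta), a sample size of 16 in each arm" and concludes that this "will have 80% power to detect a difference in means of -13.7 mmHg, using a paired t-test with a 0.05 two-sided significance level".

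**The concern.** A paired t-test and McNemar's test both need the same patient, or a matched patient, observed under each treatment. This design does not supply that. The methods named are those of a crossover trial, and the reference to treatment order in Section 5.0 reads the same way.

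Three things are at stake.
- **Aim 2 and hypotensive events.** Symptoms, recovery time and hypotensive events have no analysis that can be run as written. The analyst would have to choose a replacement later, or pair unrelated patients, in which case the result depends on the pairing chosen.
- **The supplementary effect.** With no patient on both treatments, a within-subject difference can only be a before-after change within an arm. That is not the randomised comparison, yet it could be reported as the treatment effect.
- **Power.** The stated 80% does not belong to the test named beside it.

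**Working it through.** **1. Are there any pairs?** Planned patients: 2 × 16 = 32. Each receives one product only (Sections 5.0 and 6.0) in one course (Appendix A), and there is no matching. Lanadelumab-placebo pairs available: 0.

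- A paired t-test works on differences d = (value on lanadelumab − value on placebo) within a pair. No such d exists.
- McNemar's test works on the discordant pairs, those with an event under one treatment only. No such pairs exist.
- A within-subject mean difference exists only as post-dose minus pre-dose. Even that needs a pre-dose value. Appendix A has one on Day 0 for recovery time and the six-minute walk. For the symptom score it first schedules the questionnaire on Day 1, after the first dose. Table 1 lists the questionnaire without days, so it does not settle the matter.

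**2. Reproducing the sample size.** Inputs from Section 10.0 a: difference 13.7 mmHg, SD 13.6 mmHg, two-sided α = 0.05, 16 per arm, 80% power. Standardised difference: 13.7 / 13.6 = 1.007.

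*Two-sample, normal approximation:* n per arm = 2 × (1.960 + 0.842)² × (13.6 / 13.7)² = 15.47, rounded up to 16. This reproduces the plan's number; power at 16 per arm is 81.3%.

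*Two-sample t:* noncentrality = 13.7 / (13.6 × √(2/16)) = 2.85 on 30 df.

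*Paired t, 16 pairs, SD of differences 13.6:* noncentrality = 13.7 / (13.6 / √16) = 4.03 on 15 df.

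| Calculation | Power at n = 16 | n for 80% power | Detectable difference at 80%, n = 16 |
|---|---|---|---|
| Two-sample t (n per arm) | 78.7% | 16.49, so 17 (81.3%) | 13.9 mmHg |
| Paired t (n pairs) | 96.4% | 9.83, so 10 | 10.2 mmHg |

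The stated 16 per arm and 80% match the two-sample calculation and not the paired one.

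**3. What if patients were paired arbitrarily?** For unrelated patients the SD of a difference is 13.6 × √2 = 19.23 mmHg. The noncentrality stays at 13.7 / (19.23 / √16) = 2.85, but the df fall from 30 to 15 and power falls from 78.7% to 75.9%. Pairing gains nothing. These figures use the blood-pressure inputs; the documents give no SDs for the secondary endpoints, so the effect on those cannot be put in numbers.

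**4. How much depends on the meaning of 13.6 mmHg?** The plan calls it both an SD of differences and a pooled SD of the delta. If it were the SD of within-patient differences between treatments, the per-arm SD would be 13.6 / √(2(1 − r)), where r is a within-patient correlation that the documents do not give. For assumed values:

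| Assumed r | Per-arm SD (mmHg) | Two-sample power, 16 per arm |
|---|---|---|
| 0.3 | 11.5 | 90% |
| 0.5 | 13.6 | 79% |
| 0.7 | 17.6 | 57% |

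With 16 per arm, 80% power for 13.7 mmHg requires a per-arm SD of 13.4 mmHg or less.

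**The case against.** - **The primary analysis is sound.** This stands. A fixed treatment effect with a random subject effect suits a parallel design. But that model is specified only for blood pressure, so it does not cover Aim 2 or the hypotensive events.
- **The paired wording may mean change from baseline.** It cannot for the two tests, since both are stated as comparisons of lanadelumab with placebo. For the supplementary estimate that reading is possible, but it is not the randomised contrast.
- **The plan allows non-parametric tests.** Only when normality fails, and it does not say they would be unpaired. McNemar's test has no alternative.
- **The harm is small.** A pairing fixed in advance would still give a valid test, at a cost of about 3 points of power on the blood-pressure figures. That is fair, but no pairing is specified. The main harm is that the secondary analysis is left to be chosen later.
- **The shortfall from 80% depends on the method.** This also stands. The normal approximation gives 81.3% and the t calculation 78.7%. The gap from 80% is not a defect in itself; the wrong test name and the ambiguous SD are.
- **The sample size may not be right at all.** This stands as a condition. The SD comes from preliminary icatibant data, and the documents do not say whether those were paired, so the adequacy of 16 per arm rests on 13.6 mmHg being the per-arm SD.

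**Conclusion.** The concern holds and the text must be corrected. The two named tests and the within-subject estimate cannot compare lanadelumab with placebo in this trial, because 0 of 32 planned patients contribute a pair. This rests only on the documents' own description of the design and needs no numerical assumption.

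The power sentence carries the wrong test name. Its figures fit a two-sample comparison (78.7% by t, 81.3% by normal approximation) and not a paired one (96.4%). On the assumption that 13.6 mmHg is the between-patient SD of the change within each arm, the planned size is about right for the actual design. If it is something else, the power is not known from the documents.

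**What to change.** 1. **Continuous secondary endpoints:** replace the paired t-test with an unpaired between-arm comparison. This can be a two-sample t-test, a Wilcoxon rank-sum test if normality fails, or analysis of covariance where a pre-dose value is collected. Appendix A provides one for recovery time and the six-minute walk but shows none for the symptom score.
2. **Binary endpoints:** replace McNemar's test with Fisher's exact test or logistic regression, applied to one yes/no outcome per patient. If the number of events or individual sessions are analysed instead, state the unit and use a method that allows for repeated sessions within a patient.
3. **Supplementary estimate:** replace the within-subject difference with the between-arm difference and its 95% confidence interval.
4. **Power sentence:** state the source of 13.6 mmHg and whether it is the per-arm SD of the change. If it is, restate the calculation as a two-sample t-test with 16 per arm: about 79% power for 13.7 mmHg, or 80% for 13.9 mmHg. If it is not, recompute.
5. **Section 5.0:** say that patients are randomised to a treatment arm, not an order.

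The primary mixed model need not change on this account.

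**Cost:** wording only, with no new data. No patients are added if about 79% power is accepted and the SD is confirmed. A full 80% by the t calculation needs 17 per arm, two more patients in all.

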## 6.0 Study Procedures

### Study protocol

After obtaining consent, study subjects will undergo the following procedures.

**COVID-19 precautions prior to and during visits.** Pre-visit phone call – we will contact the patient before all of their study visits to ask a series of COVID-19-related screening questions. Depending on their answers, we will continue with the study visit or postpone for another time. The patient will be asked to wear a face covering during all portions of their study visits in which they are in the presence of hospital staff. We will also encourage frequent hand washing and/or provide alcohol-based hand sanitizer.

Subjects will participate in a randomized, parallel-group, double-blind, placebo-controlled study in which they will receive two doses of placebo or 300 mg of lanadelumab subcutaneously. Participants will continue their usual medications throughout the study. One week (Day -7) before the administration of the first dose of the study drug, we will conduct a study visit at the hemodialysis unit. During this visit, we will give the participants a physical activity monitor to be worn for at least 5 consecutive days and will obtain baseline blood samples. During a second study visit at the dialysis unit (Day -1), we would obtain a second baseline blood sample one to three days before the administration of the first dose of the study drug. In this visit, we will also measure

muscle oxygenation using near-infrared spectroscopy (NIRS). Patients will be then asked to come to the Vanderbilt Clinical Research Center (CRC) on a non-dialysis day. During this visit (Day 0), we will obtain a detailed history, perform a physical examination, administer a quality of life (QOL) questionnaire, obtain the dialysis recovery time, and evaluate body composition and physical performance. We will then administer the first dose of the study drug and monitor the appearance of any Type I (immediate) hypersensitivity reaction for two hours before discharging patients from the CRC. We will repeat the same protocol, as outlined for Day 0 and administer the second dose of the study drug two weeks later at the CRC (Day 14).

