### **Physical performance tests**

Physical performance tests will include the six-minute walk test (6MWT), physical battery (gait speed and chair stand tests), and the handgrip strength, and they will be performed as previously described. Briefly, the 6MWT consists of instructing the patients to walk back and forth on a 30-meter corridor. The distance will be recorded in meters. Handgrip strength will be assessed in both hands using a dynamometer. The mean from three consecutive efforts will be used for the analysis.

Repeated chair stands: The participants will be asked to move from a sitting position to a standing position on a 42-cm high chair as quickly as possible five times. Time to complete the five repetitions will be recorded.

Gait speed: it will be performed on a 20-meter straight path, with 5 m for acceleration, 10 m for steady state walking, and 5 m for deceleration. Time will be measured by a stopwatch as the patient reaches the markers and the end of the path. The physical battery will be evaluated using standardized tests, and the results will be scored accordingly to complete the assessment of physical performance.

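### The paired t-test named for the secondary endpoints has no pairs across parallel arms and makes no use of the Day 0 values; a between-arm comparison adjusted for Day 0 would fit the design and may gain precision

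*Combined protocol and SAP*

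**What the plan says.** **Design.** Section 6.0, Study protocol: "Subjects will participate in a randomized, parallel-group, double-blind, placebo-controlled study". Each patient receives one treatment only.

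**Day 0.** At the clinical research center visit, staff will "administer a quality of life (QOL) questionnaire, obtain the dialysis recovery time, and evaluate body composition and physical performance". Only after that: "We will then administer the first dose of the study drug". The walk test is among the measures taken: "Physical performance tests will include the six-minute walk test (6MWT"). These are therefore true pre-dose values.

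**Follow-up.** For Day 14: "We will repeat the same protocol, as outlined for Day 0 and administer the second dose of the study drug two weeks later". On Day 43 recovery time and the QOL questionnaire are repeated but the walk test is not. The Study protocol text and the footnotes to Appendix A agree on that, so Day 14 is the only post-dose walk distance.

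**Analysis.** Section 10.0 b counts among the secondary endpoints "the time to recover after HD, symptoms associated with DIH, and the distance walked during the six-minute walk test". The method is: "For the secondary endpoints, a paired t-test will be performed (lanadelumab vs placebo"). The fallback is: "If the normality of the data is violated, we will use non-parametric tests". Neither sentence has a baseline term. Covariates are mentioned only as something the mixed models allow, and those models are assigned to blood pressure. KDQOL is collected but is not listed as an endpoint in section 10.0.

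**The concern.** Two gaps meet in one sentence of the plan.

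First, a paired test of lanadelumab against placebo needs pairs, and a parallel-group trial has none across arms.

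Second, someone repairing only that would probably write a two-sample t-test of follow-up values. That test is valid, but it sets aside a pre-dose measurement that every patient is already scheduled to give. With 16 patients per arm and, for the walk test, one post-dose value, the patient's own baseline is the most obvious source of extra precision. Recovery time matters most here because it is named in Specific Aim 2. The walk test appears in neither aim.

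What is at stake is the width of the intervals for these endpoints. There is also some freedom of choice: if the plan does not say whether to adjust, that decision is left until the data are in hand.

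**Working it through.** **1. The plan's own sample size.** Section 10.0 a gives 16 per arm for a blood pressure difference of 13.7 mmHg, SD 13.6 mmHg, 80% power and two-sided 0.05, and it names a paired t-test.

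- Independent groups, normal approximation: n = 2(1.960 + 0.842)² × (13.6/13.7)² = 2 × 7.85 × 0.985 = 15.5, so 16 per arm. This reproduces the figure.
- Independent groups, t-based: 16.5, so 17 per arm; power at 16 is 78.7%.
- Paired t-test as named: 9.8, so 10 pairs; power with 16 pairs is 96.4%.

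The stated 16 is thus a two-sample number, consistent with the parallel design and not with the paired wording. No SD, effect size or power is given for any secondary endpoint, so only relative gains can be computed below.

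**2. ANCOVA against an unadjusted two-sample t-test.** The correlation r between Day 0 and follow-up is an assumption, so it is shown over a range. With n = 16 per arm:

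- variance factor = (1 − r²) × [1 + 1/(2n − 4)] = (1 − r²) × (1 + 1/28) = (1 − r²) × 1.036
- CI width ratio = √(variance factor) × t(0.975; 29 df)/t(0.975; 30 df) = √(variance factor) × 2.045/2.042
- equivalent unadjusted n per arm = 16/(variance factor)

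| r (assumed) | Variance factor | CI width ratio | Change in width | Equivalent n per arm |
|---|---|---|---|---|
| 0 | 1.036 | 1.019 | 2% wider | 15.4 |
| 0.3 | 0.943 | 0.972 | 3% narrower | 17.0 |
| 0.5 | 0.777 | 0.883 | 12% narrower | 20.6 |
| 0.7 | 0.528 | 0.728 | 27% narrower | 30.3 |
| 0.8 | 0.373 | 0.612 | 39% narrower | 42.9 |

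**3. ANCOVA against a t-test on change from Day 0.** With equal SDs at the two visits, the change score has variance factor 2(1 − r). The ratio of ANCOVA to change score is (1 − r²)/[2(1 − r)] = (1 + r)/2, before the small-sample correction. The CI width ratio is its square root.

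| r (assumed) | (1 + r)/2 | CI width ratio | Change in width |
|---|---|---|---|
| 0.5 | 0.75 | 0.866 | 13% narrower |
| 0.7 | 0.85 | 0.922 | 8% narrower |
| 0.8 | 0.90 | 0.949 | 5% narrower |
| 0.9 | 0.95 | 0.975 | about 3% narrower |

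The factor 1.036 trims these gains. At r = 0.9, √(0.95 × 1.036) = 0.992, which leaves about 1%. At r = 0.5 the change score itself gains nothing over ignoring baseline, since 2(1 − 0.5) = 1.

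**4. How far the figures carry.** They are for a linear model. In section 6.0, Dialysis Recovery Time, verbal answers are converted to 720, 1440 or 2160 minutes, so values will heap. If recovery time is analyzed by ranks or by an ordinal model, these percentages do not transfer, and neither method yields a difference in minutes.

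**5. Which follow-up value.** Section 10.0 a defines the recovery-time endpoint as an average over the second treatment week. Appendix A schedules the question only on Days 0, 14 and 43. The outcome to be adjusted is therefore not settled for recovery time. For the walk test it can only be Day 14.

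**The case against.** The strongest reply has four parts.

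- **The plan does not choose to discard baseline.** It names a paired test that cannot be run across arms, and it never says whether the secondary variable is a raw follow-up value or a change from Day 0. This stands: the silence is an omission. Nearby wording about within-subject differences would even permit a change-score reading, and against that comparator the gain is modest (step 3). A reader might infer that the plan prescribes a plain between-arm t-test on follow-up values; the text does not say so.
- **The correlations have no source in the documents.** This also stands. A high r is plausible for a walk test repeated after two weeks, but that is a judgment. Recovery time is a single recalled answer with coarse conversions, and its r may be lower. A reader might infer that much of the attainable precision is certainly lost; at r = 0.3 the loss is about 3% of CI width, and at r = 0 adjustment costs about 2%.
- **Randomization already protects the comparison.** Correct. An unadjusted two-sample test keeps its 5% level, and chance baseline imbalance is reflected in its standard error. A reader might infer that imbalance biases the result; it does not.
- **The plan warns against over-fitting.** One prespecified covariate with 32 patients costs one degree of freedom, which is not what that caution is about.

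It can also be said that correcting the pairing error means rewriting this sentence anyway. That is a reason to make both changes in one edit. It does not answer the point, because the simplest correction would still leave Day 0 unused.

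**Conclusion.** The point holds as a precision point with a design mismatch underneath it. The documents establish that pre-dose values exist for recovery time, walk distance and KDQOL, that the named paired test does not fit a parallel-group trial, and that no analysis stated for the secondary endpoints uses the Day 0 value.

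The size of the gain is conditional. Against an unadjusted two-sample test it runs from 2% wider to 39% narrower intervals over r = 0 to 0.8. Against change scores it is about 13% to 3% narrower over r = 0.5 to 0.9, before small-sample correction. Both ranges assume a linear model, 16 per arm and, for change scores, equal SDs at the two visits. They do not apply to recovery time if it is analyzed ordinally.

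Nothing here shows bias or an invalid test once the pairing is corrected, and no power is claimed for these endpoints. The case for acting is that the possible loss is trivial, the possible gain is material, and the data are already scheduled.

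**What to change.** Replace the paired t-test sentence in section 10.0 b, for endpoints that have a Day 0 value, along these lines:

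- **Six-minute walk distance:** compare arms by ANCOVA of the Day 14 value on treatment and the Day 0 value; report the adjusted difference with its 95% CI. Treat KDQOL in the same way if it is to be reported, naming its visit (Day 14 or Day 43).
- **Recovery time:** first reconcile the second-week average in section 10.0 a with the Day 0, 14 and 43 schedule in Appendix A, and name the visit. Then prespecify one model and the effect measure that goes with it, for example proportional odds with Day 0 recovery time as covariate, reported as an odds ratio with its 95% CI.
- **Fallback:** name the method in advance in place of the open reference to non-parametric tests, and keep the Day 0 value in it.

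The cost is SAP wording and one degree of freedom in each linear model. No new visits or measurements are needed.
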